Appendix D

VM202 Test Material Preparation and Administration

1. Selection of injection sites

Identify occluded sites using contrast magnetic resonance (MRA) or computerized tomography (CTA) angiography. Select injection sites with the objective of inducing the formation of bridging collaterals from areas with normal blood flow and improving runin. Therefore, areas adjacent to the occluded sites and areas where blood flow through good collateral blood vessels decreases are desirable as injection sites. Documentation of injections sites will be indicated by placing an **X** on the diagram provided in the CRF and shown below.

2. Test material administration

On Day 1 and Day 15 the subject will receive test material. The study treatment will be administered as up to 8 injections. A fine needle (e.g. 27 gauge, 1") suitable for IM injections will be used; 2.0 ml will be administered per injection site (total volume of 8 or 16 ml per administration, determined by cohort assignment). Inject the entire amount of the drug in about 20-30 seconds. Immediately after completion of injection, lightly press the injection site with the finger head in order to prevent reflux. Do not massage the injection site.

3. Second test material administration

Each administration will be given at least 2 cm from the previous injection site. It is recommended that an indelible marker be used to mark the location of previous injections to ensure that repeat injections are not delivered to exact same location with the subsequent administration.

Injection Documentation Diagram

Indicate on drawing by marking an X at each injection site

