Title: A Phase I, Dose-Escalation Study to Assess the Safety and

Tolerability of VM202 in Subjects with Critical Limb Ischemia

Study Phase: I

Treatment Duration: Study drug administered on two separate occasions, Days 1 and

15. Each treatment is divided into 4 or 8 IM injections.

Study Duration: 30 months

Individual Subject

Enrollment: 12 months

Name of Drug: VM202

Dosage: Cohort I-VM202 2 mg with the first half of the total dose given

on Day 1 and the second half given on Day 15

Cohort II-VM202 4 mg with the first half of the total dose given

on Day 1 and the second half given on Day 15

Cohort III-VM202 8 mg with the first half of the total dose

given on Day 1 and the second half given on Day 15

Cohort IV-VM202 16 mg with the first half of the total dose

given on Day 1 and the second half given on Day 15

Route of Administration: Intramuscular (IM) injection into the muscle closest to the

affected area. Volume determined by dose.

Study Objectives: To evaluate VM202 administered by intramuscular injection in

subjects with critical limb ischemia for the following:

1. Safety

2. Tolerability

3. Preliminary efficacy

Study Design: This is a prospective, dose-escalation study to evaluate the safety

and tolerability of intramuscular VM202 in subjects with critical

limb ischemia.

The study will consist of four (4) cohorts with a total of 3 subjects enrolled in each cohort to VM202. For each dose cohort, VM202 will be administered as a local intramuscular

injection in 2 divided doses with a 2-week interval between the injections. Preliminary efficacy (hemodynamic assessments), safety and tolerability will be evaluated at Baseline (screening) and at designated time points throughout the study.

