6.0 Treatment of Subjects

6.1 Treatments Administered

This study will be conducted using the dosing schedule shown in Table 6-1. Projected doses are based on an 80 kg human. The dose has been selected based upon assumptions that the allometric scaling of terminal $t\frac{1}{2}$ will apply.

Table 6-1 Treatments

Cohort	Number of	Total Dose	Number of	Time of
	Subjects	(mg)	Doses	Dosing
	3	2	2; each divided	
I			among 8	Day 1, Day 15
			injection sites	
II	3	4	2; each divided	
			among 16	Day 1, Day 15
			injection sites	
III	3	8	2; each divided	
			among 16	Day 1, Day 15
		injection sites		
	3	16	2, each divided	
IV			among 16	Day 1, Day 15
			injection sites	

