6.1.1 Treatment Regimen and Follow-Up

For each cohort, VM202 will be administered as either 8 or 16 local intramuscular injections to the affected limb in 2 divided doses with a 2-week interval between the injections. A total of 4 or 8 different injection sites will be arbitrarily chosen dependent on the dose and the location of the occluded vessels. The location of the injections sites will be documented on a leg diagram provided in the CRF. Each injection will contain a maximum of 2 ml (regardless of weight) and will be injected at each site slowly for about 20 to 30 seconds as described in Appendix D.

VM202 is provided in a sterile glass vial containing lyophilized 2.0 mg of study drug. Before use, it will be reconstituted with 4 ml of water for injection (WFI). Each reconstituted vial is only to be used for one patient. After the vial is reconstituted the following dosing information is applicable:

Cohort I has a total dose of 2.0 mg which is 1.0 mg per administration (0.25 mg per syringe in 0.5 ml for 4 injection sites per administration)

Cohort II has a total dose of 4.0 mg which is 2.0 mg per administration (0.25 mg per syringe in 0.5 ml for 8 injection sites per administration)

Cohort III has a total dose of 8.0 mg which is 4.0 mg per administration (0.5 mg per syringe in 1.0 ml for 8 injection sites per administration)

Cohort IV has a total dose of 16.0 mg which is 8.0 mg per administration (1.0 mg per syringe in 2.0 ml for 8 injection sites per administration)

VM202 will be administered in a 1.0 ml syringe for Cohorts I, II and III and a 3.0 ml syringe for Cohort IV. The volume of medication to be used for the four dose cohorts is as follows:

- Cohort I-fill 4 syringes with 0.5 ml per syringe
- Cohort II-fill 8 syringes with 0.5 ml per syringe
- Cohort III-fill 8 syringes with 1.0 ml per syringe
- Cohort IV-fill 8 syringes with 2.0 ml per syringe

The same volume will be used for both the first and the second doses (series of either 4 or 8 injections in only one affected leg) for each subject.

Injection volume by ml

Cohort	Dose	Volume/ administration	Volume/ injection site	Injections/Administration
I	1mg	2ml	0.5ml	4
II	2mg	4ml	0.5ml	8
III	4mg	8ml	1ml	8
IV	8mg	16ml	2ml	8

Injection volume by units

Cohort	Dose	Volume/ administration	Volume/ injection site	Injections/Administration
I	1mg	200units	50units	4
II	2mg	400units	50units	8
III	4mg	800units	100units	8
IV	8mg	1600units	200units	8

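### Appendix D's 2.0 ml per site and 8 or 16 ml per administration cannot deliver the Cohort I or II dose set in Section 6.1.1, and the injection counts in 6.2.2 and Table 6-1 also conflict with it

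*Protocol*

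**What the plan says.** **Volume, Protocol 6.1.1.** Each vial holds 2.0 mg, and "it will be reconstituted with 4 ml of water for injection (WFI"). The cohort text, the syringe-fill list (for example "Cohort I-fill 4 syringes with 0.5 ml per syringe") and the two volume tables agree with each other: 0.5, 0.5, 1.0 and 2.0 ml per site for Cohorts I to IV, in 4, 8, 8 and 8 injections per administration. On equipment: "VM202 will be administered in a 1.0 ml syringe for Cohorts I, II and III and a 3.0 ml syringe for Cohort IV". Here 2 ml is only a ceiling: "Each injection will contain a maximum of 2 ml (regardless of weight").

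**Volume, Protocol Appendix D, item 2.** Treatment is given as up to 8 injections, and "2.0 ml will be administered per injection site (total volume of 8 or 16 ml per administration, determined by cohort assignment").

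**Injection counts.**
- Synopsis: "Each treatment is divided into 4 or 8 IM injections".
- Section 6.1.1, over both doses: "VM202 will be administered as either 8 or 16 local intramuscular injections to the affected limb in 2 divided doses".
- Section 6.1 introduces its table with "This study will be conducted using the dosing schedule shown in Table 6-1". Table 6-1 then divides each of the two doses among 8 sites (Cohort I) or 16 sites (Cohorts II to IV).
- Section 6.2.2 (Day 1) calls for 8 injections with no exception for Cohort I. Section 6.2.4 carries the Day 1 manner of administration over to Day 15.

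**SAP.** Section 10.1 tabulates whether the total volume was given per protocol. It also plans to summarise the continuous volume, but names minutes as the unit. Table 11 has no volume row, only an administration-time row labelled in mg.

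**The concern.** Appendix D appears to have turned the 2 ml ceiling of 6.1.1 into a fixed volume per site. The two totals it allows are the 6.1.1 totals for Cohorts III and IV, so it contains no volume that fits Cohort I or II.

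Dose is the planned difference between cohorts. The escalation decisions, the assignment of the MTD and every dose column in the SAP tables depend on it. Volume per site matters in its own right: injection site reactions are a primary safety endpoint, and tissue necrosis at the injection site is a dose-limiting toxicity.

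The SAP's per-protocol volume check has no single reference while two protocol sections give different volumes. The continuous summary that could show what was given carries the wrong unit.

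**Working it through.** **Inputs.** From 6.1.1: 2.0 mg per vial, 4 ml reconstitution, and ml per site and sites per administration by cohort. From Appendix D: 2.0 ml per site, and 8 or 16 ml in total. There are two administrations, on Days 1 and 15.

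**Formulas.** Concentration = 2.0 mg / 4 ml = 0.5 mg/ml. Dose per administration = sites × ml per site × 0.5 mg/ml. Total dose = 2 × dose per administration.

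**1. The plan's own figures (6.1.1) reproduce.**

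| Cohort | Sites × ml | ml per administration | mg per administration | Total mg |
|---|---|---|---|---|
| I | 4 × 0.5 | 2 | 1 | 2 |
| II | 8 × 0.5 | 4 | 2 | 4 |
| III | 8 × 1.0 | 8 | 4 | 8 |
| IV | 8 × 2.0 | 16 | 8 | 16 |

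Each escalation step is 2×.

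**2. Appendix D on its most favourable reading.** The smaller total gives 8 ml × 0.5 mg/ml = 4 mg per administration. Against Cohort I this is 4/1 = 4×, and against Cohort II 4/2 = 2×. The larger total gives 16 × 0.5 = 8 mg, which is 8× and 4× respectively.

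**3. Reading A: 2.0 ml at the 6.1.1 site counts.** Volumes are 4 × 2, 8 × 2, 8 × 2 and 8 × 2 = 8, 16, 16 and 16 ml. Total doses are 8, 16, 16 and 16 mg, or 4×, 4×, 2× and 1× plan. The escalation steps become 2×, 1× and 1×, so Cohorts II to IV coincide.

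**4. Reading B: 8 ml for Cohorts I to III and 16 ml for Cohort IV.** Total doses are 8, 8, 8 and 16 mg, or 4×, 2×, 1× and 1× plan. The steps become 1×, 1× and 2×, so Cohorts I to III coincide. Cohort III's dose is on plan, but 8 ml at 2.0 ml per site means 8/2.0 = 4 sites, not 8.

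**5. Could dilution reconcile the sections?** For Cohort I, 1 mg in 8 ml needs 0.125 mg/ml. For Cohort II, 2 mg needs 0.25 mg/ml in 8 ml or 0.125 mg/ml in 16 ml. The protocol provides for no further dilution, and 6.1.1 fixes 0.25 mg in 0.5 ml per syringe for both cohorts.

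**6. Injection counts, which are separate from the volume conflict.**
- Section 6.2.2 in Cohort I: eight 0.5 ml injections on both days give 8 × 0.5 × 0.5 × 2 = 4 mg, the Cohort II dose. If the planned 1 mg is instead shared over 8 sites (0.125 mg in 0.25 ml each), the total stays at 2 mg. Cohorts II to IV are unaffected.
- Table 6-1: 8, 16, 16 and 16 sites per dose against 4, 8, 8 and 8 in 6.1.1, a factor of 2 in every cohort. Its total-dose column (2, 4, 8, 16 mg) is correct.

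**The case against.** The strongest reply is that 6.1.1 defines the dose completely and consistently, and that the Appendix D figure is its ceiling loosely copied. A 2.0 ml injection does not fit the 1.0 ml syringe specified for Cohorts I to III, and a pharmacist prepares the drug under detailed sponsor instructions. This stands as an argument that misdosing is improbable, and it makes Readings A and B hypothetical. It does not remove the conflict: no clause gives 6.1.1 precedence, and 6.1.1 itself sends the reader to Appendix D.

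A second reply is that the Version 5.0 rationale cites safety in the first two cohorts, so Cohorts I and II had already been dosed, while 8 and 16 ml are the right totals for III and IV. This limits the prospective harm. It leaves the 4-versus-8-site conflict in Cohort III, and it makes checking the doses already given more relevant.

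Third, the count errors are small. Section 6.2.2 refers back to the earlier description and is wrong only for Cohort I. Table 6-1's counts equal the two-dose totals in 6.1.1 and look like a per-dose wording slip. That is fair, and neither count proves a dose error.

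Fourth, the actual amounts are recoverable from pharmacy records and from the SAP's drug administration listing, and the SAP unit labels are separate mistakes not caused by Appendix D. Also fair. But the planned exposure table as laid out still gives no usable volume or dose summary.

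**Conclusion.** The concern holds. At the only concentration the protocol gives, neither Appendix D total delivers the Cohort I or Cohort II dose; the smallest discrepancy is 4× for Cohort I and 2× for Cohort II. Cohort III agrees on total volume only with half the planned sites, and Cohort IV alone agrees fully. The counts in 6.2.2 (Cohort I) and Table 6-1 (all cohorts) are also wrong against 6.1.1.

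This rests on 6.1.1 being the intended regimen, which its internal consistency and the stated total doses support, and on reconstitution at 0.5 mg/ml with no further dilution. It is a contradiction in the dosing instructions and not evidence that anyone was overdosed. In a dose-escalation trial it must be corrected, because the volume given defines the cohorts.

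**What to change.** - **Appendix D:** replace the volume sentence with the 6.1.1 table or a pointer to it. Cohort I 4 × 0.5 ml (2 ml, 1 mg); II 8 × 0.5 ml (4 ml, 2 mg); III 8 × 1.0 ml (8 ml, 4 mg); IV 8 × 2.0 ml (16 ml, 8 mg); no site above 2 ml. The sponsor should confirm that 6.1.1 governs.
- **Section 6.2.2:** 4 injections in Cohort I, 8 in Cohorts II to IV.
- **Table 6-1:** 4 sites per dose in Cohort I, 8 in Cohorts II to IV.
- **SAP 10.1 and Table 11:** report volume in ml and dose in mg actually given, with the 6.1.1 volume as the per-protocol reference.
- **Cohorts already dosed:** confirm the volumes from pharmacy records and report the actual dose.

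The cost is one appendix sentence, one count, one table column, a few SAP labels and a check of records the protocol already requires.

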Appendix EReasons for Modifications

Type of Modification to Protocol	Affected	Reason(s) for the
(A: Added, C: Changed, D: Deleted)	Pages	Modification(s)
Version 2.0 Modifications		
Cover page (C) Section 6.3 Autopsy (C) Section 8.1.5 Documentation of AEs and SAEs (C) Section 8.1.6 Follow-Up of AEs and SAEs (C) Section 8.1.7 Immediate Reporting of SAEs (C) Section 8.1.8 Transmission of SAE Reports (C) Section 10 Quality Control and QA (C) Formerly:	41, 42, 43,	Updated the contact information for the medical monitor and CRO.
Signature Page (C) Formerly: Version Number: 1.0 Modified to: Amended Version Number: 2.0 Formerly: IND Number: Modified to: IND Number: 13158	ii	Changed amended version number and added IND number.
Protocol Synopsis (D) Formerly: The Quality of Life questionnaire will be done on Days 28, 59 and 180 (± 2 days). Section 4.1.2 Secondary Efficacy Endpoints (D) Formerly: Change from Baseline in quality of life, as measured by the SF-36, at Days 15, 28, 59, 180 and 365. Section 4.2.3 Schedule of Assessments Table 4-1 (D)	8, 18, 21, 22, 23, 24,	Deleted QOL because not statistically relevant for Phase I sample size.

V 1	Affected	Reason(s) for the
(A: Added, C: Changed, D: Deleted)	Pages	Modification(s)
Section 6.2.1 Screening Day (D)		
Section 6.2.5 Day 15 (D)		
Section 6.2.8 Day 28 (D)		
Section 6.2.9 Day 59 (D)		
Section 6.2.11 Day 180 (D)		
Section 6.2.12 Day 365 (D)		
Section 6.2.15 Early Termination Visits (D)		
Formerly:		
Quality of Life (QOL)		
Section 7.2.6 Quality of Life Score (D)		
Formerly:		
Quality of Life (QOL) will be measured using the		
Medical Outcomes Study short form (SF-36). ¹⁰ The		
survey should be self-administered by the subject or		
administered by the Investigator or designee. The		
survey should be administered the same way each time		
it is completed. Responses will be documented on the		
CRF. If SF-36 testing falls on a study drug		
administration day, the questionnaire will be taken		
before study drug administration so that study related		
discomforts do not influence the subject's health		
perception.		
Section 9.3 Statistical Analysis (C)		
Formerly:		
Descriptive statistics (N, mean, median, SD, minimum		
and maximum values) of vascular assessments (ABI,		
TBI, Wave Form Analysis), TcPO ₂ , High Resolution		
MRA, VAS for pain, analgesic use, ulcer size and		
QOL response will be reported.		
Modified to:		
Descriptive statistics (N, mean, median, SD, minimum		
and maximum values) of vascular assessments (ABI,		
TBI, Wave Form Analysis), TcPO ₂ , High Resolution		
MRA, VAS for pain, analgesic use, and ulcer size will		
be reported.		
Protocol Synopsis (C)	xii, xiv, 8,	Extend long-term
* * /	25, 28	follow-up from 2
All subjects will be followed for two years from the	25, 20	to 5 years from the
time of the first dose of study drug administration.		time of the first
Modified to:		dose of study drug
All 4 dose cohorts will be followed for up to five years		administration

Type of Modification to Protocol	Affected	Reason(s) for the
(A: Added, C: Changed, D: Deleted)	Pages	Modification(s)
from the time of the first dose of study drug administration.		(requested by the FDA at the Oct. 31, 06 meeting).
Formerly: All subjects will be followed for two years from the time of first dose administrations. Modified to: All subjects will be followed for two years from the time of first dose administrations and will be in long term follow-up for a total of 5 years.		
Section 4.2.3 Schedule of Assessments Table 4-1 (C) Modified to include: 6Annual telephone follow-up contacts will continue for 4 years after day 365		
Delete: Annual telephone follow-up at day 365		
Section 6.2.13 Long-term Follow-Up (C) Formerly: In keeping with current recommendations by FDA to maintain a long-term follow-up on subjects who receive gene transfer therapy, safety data will be collected for one (1) additional year following the subject's completion of study-related procedures.		
Modified to: In keeping with current recommendations by FDA to maintain a long-term follow-up on subjects who receive gene transfer therapy, safety data will be collected for up to 5 years (i.e., 4 additional years following the subject's completion of study-related procedures).		
Section 6.4.2 Replacement of Study Subjects (C) Formerly: If the subject has received one or both doses of study drug, the subject will remain in the study through the two year follow-up period. Modified to:		
If the subject has received one or both doses of study drug, the subject will remain in the study through the five year follow-up period.		
Protocol Synopsis (C)	xii, 7, 10,	Clarification of the

Type of Modification to Protocol	Affected	Reason(s) for the
(A: Added, C: Changed, D: Deleted)	Pages	Modification(s)
Formerly: If a dose limiting toxicity is observed at any dose group, three additional subjects will be added to the dose cohort in whom the toxicity was observed and to all lower dose cohorts and all evaluations will be repeated for these additional subjects. Modified to: If a dose limiting toxicity is observed in one subject in any dose group, three additional subjects will be added to the dose cohort in which the toxicity was observed. If no additional DLTs are observed in the 6 subjects in this dose level, it will be considered the Maximum Tolerated Dose (MTD). If a DLT occurs in 2/6 subjects, then 3 additional subjects will be enrolled at the previous dose level. If no DLTs occur at this level it will be considered the MTD.	17, 35	standard 3+3 Phase 1 trial design (requested by the FDA at the Jan. 06 Pre-IND meeting).
Section 4.2.2 Number of Subjects (C) Formerly: There will 12 subjects selected at one site for participation in this study with 3 subjects treated in each of four (4) study cohorts. Modified to: There will 12-15 subjects selected at one site for participation in this study with 3 subjects treated in each of four (4) study cohorts. There will be an additional 3 patients treated in a cohort if 1/3 subjects experiences a DLT and if the DSMC recommends continuing the trial.		
Section 4.5 Treatments (A) Addition: If a DLT occurs in 2/6 subjects then 3 additional subjects will be treated at the previous dose level and if no DLT occurs in that cohort, it will be considered the MTD.		
Section 6.1.1 Treatment Regimen and Follow-Up (C) Formerly: In the event that a dose limiting toxicity (DLT) is determined after the safety review between Cohort I and Cohort II, between Cohort II and Cohort III or between Cohort III and Cohort IV, there will be 3 additional subjects treated at the same dose and at all		

Type of Modification to Protocol	Affected	Reason(s) for the
(A: Added, C: Changed, D: Deleted)	Pages	Modification(s)
lower doses (either 2 mg only, 2 mg and 4 mg or 2		
mg, 4 mg and 8 mg)		
Modified to:		
In the event that a DLT is determined after the safety		
review in any cohort , there will be 3 additional		
subjects treated at the same dose level. If no further		
DLTs are observed in the 6 subjects and the DSMC		
approves dose escalation, then subjects can be		
enrolled to the next higher dose level. If 2/6		
subjects experience a DLT then the preceding dose		
level treatment group will be considered the MTD.		
Section 7.1.9 Dose Limiting Toxicity (DLT) (C)		
Formerly:		
In the event of a DLT at any dose, 3 additional		
subjects will be treated at that dose and at all lower		
doses.		
Modified to:		
In the event of a DLT at any dose, 3 additional subjects will be added to the dose cohort in which		
the toxicity was observed. If no additional DLTs are		
observed in the 6 subjects in this dose level, it will be		
considered the Maximum Tolerated Dose (MTD). If		
a DLT occurs in 2/6 patients, then 3 additional		
subjects will be enrolled at the previous dose level.		
If no DLTs occur at this level it will be considered		
the MTD.		
Protocol Synopsis (C)	xiii, 8, 11,	Add CT scan of
Formerly:	18, 25, 27	the chest to the
Chest X-ray	-,,,	List of
Modified to:		Assessments as CT
Chest X-ray or CT scan of the chest (if the subject		scan will be
has a previous history of tobacco use, a CT scan		performed instead
will be performed instead of the chest X-ray)		of the chest X-ray
		if the subject has a
For subjects with isohomic ulars a photograph of the		previous history of
For subjects with ischemic ulcer, a photograph of the		tobacco use
ulcer will be obtained. Safety laboratory (hematology, chemistry, urinalysis), tumor marker tests, infection		(requested by the Institutional
tests, chest X-ray, and ECG will also be done at		Biosafety
Baseline.		Committee (Oct.
1	1	

Type of Modification to Protocol	Affected	Reason(s) for the
(A: Added, C: Changed, D: Deleted)	Pages	Modification(s)
Modified to:		06).
For subjects with ischemic ulcer, a photograph of the		
ulcer will be obtained. Safety laboratory (hematology,		
chemistry, urinalysis), tumor marker tests, infection		
tests, chest X-ray or CT scan of the chest (if the		
subject has a previous history of tobacco use, a CT		
scan will be performed instead of the chest X-ray),		
and ECG will also be done at Baseline.		
Section 4.2.3 Schedule of Assessments Table 4-1 (C)		
Formerly:		
Chest X-ray		
Modified to:		
Chest X-ray or CT scan of chest ¹		
CT scan of the chest instead of chest X-ray will be		
performed if previous tobacco use.		
Section 5.1 Cancer Screening (D)		
Formerly:		
Chest X-ray or CT scan of the chest within 3 months		
prior to study entry		
Modified to:		
Chest X-ray or CT scan of the chest (if the subject		
has a previous history of tobacco use, a CT scan		
will be performed instead of the chest X-ray) within		
3 months prior to study entry		
Section 6.2.1 Screening Day (C)		
Formerly:		
Chest X-ray (AP only)		
Modified to:		
Chest X-ray or CT scan of the chest (if the subject		
has a previous history of tobacco use, a CT scan		
will be performed instead of the chest X-ray)		
Section 6.2.12 Day 365 (A)		
Added:		
Chest X-ray or CT scan of the chest (if the subject		
has a previous history of tobacco use, a CT scan		
will be performed instead of the chest X-ray)		
Section 6.2.15 Early Termination Visits (A)		
Added:		
Chest X-ray or CT scan of the chest (if the subject		

Type of Modification to Protocol	Affected Pages	Reason(s) for the Modification(s)
(A: Added, C: Changed, D: Deleted) has a previous history of tobacco use, a CT scan will be performed instead of the chest X-ray)	1 ages	Wiodification(s)
Protocol Synopsis (C) Formerly: There will be 8 injections administered slowly for 20~40 seconds at pre-determined sites (mainly at the calf muscles) without local anesthesia Modified to: There will be 4 or 8 injections depending on the on the dose level administered slowly administered slowly for 20~40 seconds at pre-determined sites on only one affected leg (mainly at the calf muscles) without local anesthesia.	xiii, xiv, 16	Clarify that the doses are administered to only one leg (requested by the FDA at the Oct 31, 06 meeting).
Formerly: After the 2nd half of the total dose is administered (Day15), hemodynamic assessments (ABI, TBI, Wave Form Analysis), TcPO ₂ , photograph and measurement of ischemic ulcer, VAS for pain, and safety labs will also be assessed on Days 28, 59, 91, 180 and 365. Modified to: After the second dose is administered (Day15) to the leg previously injected , hemodynamic assessments (ABI, TBI, Wave Form Analysis), TcPO ₂ , photograph and measurement of ischemic ulcer, VAS for pain, and safety labs will also be assessed on Days 28, 59, 91, 180 and 365.		
Section 6.1.1 Treatment Regimen and Follow-Up (C) Formerly: The same volume should be used for both the first and the second doses (series of either 4 or 8 injections) for each subject. Modified to: The same volume will be used for both the first and the second doses (series of either 4 or 8 injections in only one affected leg) for each subject.		
Section 4.1.3 Pharmacokinetic Evaluations (D) Formerly: Pharmacokinetics of VM202 will be assessed using blood VM202 DNA concentration levels from samples obtained pre-dose and 60 minutes and 24	6, 8, 21	Deleted the time point of 24 hour post-drug administration for VM202 DNA

Type of Modification to Protocol	Affected	Reason(s) for the
(A: Added, C: Changed, D: Deleted) hours post-dose at the first and second dose administration (Day 1 and Day 15). Modified to:	Pages	Modification(s) concentration level because 1 hour post-drug
Pharmacokinetics of VM202 will be assessed using blood VM202 DNA concentration levels from samples obtained pre-dose and 60 minutes post-dose at the first and second dose administration (Day 1 and Day 15).		administration and day 8 time points are sufficient data points for this assessment.
Section 4.1.3 Pharmacokinetic Evaluations (D) Formerly: Pharmacokinetics of VM202 will be assessed using blood VM202 DNA concentration levels from samples obtained pre-dose and 60 minutes and 24 hours post-dose at the first and second dose administration (Day 1 and Day 15). Modified to:		
Pharmacokinetics of VM202 will be assessed using blood VM202 DNA concentration levels from samples obtained pre-dose and 60 minutes post-dose at the first and second dose administration (Day 1 and Day 15).		
Section 4.2.3 Schedule of Assessments Table 4-1 (C) Formerly: Blood VM202 DNA level at 1 and 24 hours post study agent administration Modified to:		
⁴ Blood VM202 DNA level at 1 hour post study agent administration		
Section 6.2.3 Day 2 (D) Formerly: 6.2.3 Day 2 The following analysis are will be professed at the		
The following evaluations will be performed at the Day 2 visit: · VM202 DNA level at 24-hours post dose · Adverse events		
Section 4.6 Duration (C) Formerly: There will be a 7-day safety evaluation that will begin 30 days after the first dose of study drug (Day 30) for cohort I. The safety evaluation (adverse events) must	10, 16	Clarification of the timing of the safety evaluation by the DSMC.

Type of Modification to Protocol	Affected	Reason(s) for the
(A: Added, C: Changed, D: Deleted)	Pages	Modification(s)
be completed prior to the beginning of the next study		
drug administration for the following study cohort (II,		
III and IV).		
Modified to:		
There will be safety evaluations that will begin 30		
days after the first dose of study drug (Day 30) for all		
cohorts. Safety evaluations to encompass 30 days		
post the first dose will be completed for each cohort and will be evaluated by the DSMC prior to dose		
escalation to the next cohort. This 30-day window		
will include a 2-week safety evaluation following		
each dose at Day 1 and 15.		
Section 6.1.1 Treatment Regimen and Follow-Up (C)		
Formerly: There will be a mandatory review of all safety data		
between the treatments of Cohort I and Cohort II,		
between Cohort III and Cohort IV. No subject may be		
enrolled in Cohort II, Cohort III or Cohort IV until the		
SRC has reviewed the data and provided a written		
notice to continue the trial to the Sponsor.		
Modified to:		
There will be a mandatory review of all safety data		
between the treatments of all dose cohorts (Cohort I-		
IV). No subject may be enrolled in subsequent		
cohorts until the DSMC has reviewed the data and		
provided a written notice to continue the trial to the Sponsor.		
Sponsor.		
Section 5.3 Exclusion Criteria (C)	12	Clarify that
Formerly:		subjects will be
Subjects with a current history of malignant neoplasm		excluded if a new
except for basal cell carcinoma of the skin and		screening finding
squamous cell carcinoma of the skin (if excised and no		of malignancy is
evidence of recurrence		observed
Modified to: Subjects with a current history or new screening		(requested by the FDA at the Oct.
finding of malignant neoplasm except for basal cell		31, 06 meeting).
carcinoma of the skin and squamous cell carcinoma of		51, 00 meeting).
the skin (if excised and no evidence of recurrence		
Section 6.2.2 Day 1 (C)	20. 24	Clarify that
Section 6.2.2 Day 1 (C) Formerly:	20, 34	Clarify that subjects will
If any of the above occurs, the subject should be		contact the site if
11 any of the above occars, the subject should be	I	Contact the Site ii

Type of Modification to Protocol	Affected	Reason(s) for the
(A: Added, C: Changed, D: Deleted)	Pages	Modification(s)
instructed to immediately return to the clinic or to go to the nearest Emergency Room for immediate treatment and evaluation. No further study drug		pain, redness or discomfort occurs between day 1 and
administration should occur in such cases. Modified to: If any of the above occurs, the subject will be		one week (requested by the FDA at the Oct.
instructed to call the clinic immediately and seek medical attention either at the clinic or to go to the nearest Emergency Room for immediate treatment and evaluation. No further study drug administration will		31, 06 meeting).
occur until it is determined if this is a DLT or as		
directed by the treating physician.		
Section 7.1.9 Dose Limiting Toxicity (DLT) (C) Formerly:		
Evidence for active tissue necrosis at the injection site within 72 hours of study drug administration Modified to:		
Evidence for active tissue necrosis at the injection site		
within two weeks of study drug administration		
Section 6.1.1 Treatment Regimen and Follow-Up (C) Formerly:	15, 62	Specify general rules and
The location of the injections sites will be documented		descriptive
photographically and on a leg diagram. Each		schematic diagram
injection will contain a maximum of 2 ml (regardless		in the protocol
of weight) and will be injected at each site slowly for		(Appendix D) and
about 20 to 40 seconds.		the CRF to serve
Modified to:		as guidance for
The location of the injections sites will be documented		choosing injection
on a leg diagram provided in the CRF . Each		sites on the leg
injection will contain a maximum of 2 ml (regardless of weight) and will be injected at each site slowly for		(requested by the FDA at the Oct.
about 20 to 40 seconds as described in Appendix D.		31, 06 meeting).
		, 00 mooning).
